7.7 RELATIONSHIP OF AES TO THE STUDY DEVICE

How any AE related to the study procedure will be reported on the Adverse Event CRF and be determined by the Principal Investigator using the following definitions:

Definite: The AE follows a reasonable temporal sequence from the time of index procedure. This includes an AE that occurs during the index procedure and during the follow-up period.

Probable: The AE follows a reasonable temporal sequence from the time of index procedure and the possibilities of factors other than the index procedure, such as underlying disease, concomitant drugs, or concurrent treatment can be excluded.

Possible: The AE follows a reasonable temporal sequence from the time of index procedure and the possibility of index procedure involvement cannot be excluded. However, other factors such as underlying disease, concomitant medications, or concurrent treatment are presumable.

Unlikely: The AE has an improbable temporal sequence from the time of index procedure, or it can be reasonably explained by other factors, including underlying disease, concomitant medication, or concurrent treatment.

Not related: The AE has no temporal sequence from the time of the index procedure, or it can be explained by other factors, including underlying disease, concomitant medication, or concurrent treatment.

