AEs should be classified according to their underlying cause, if known, (e.g., fever resulting from infection should be reported as “infection”). Concomitant AEs that are unrelated (in the clinician’s judgment) should be reported as separate events.

AE determination is based on three levels of evidence:

Level 1 – final diagnosis

Level 2 – signs

Level 3 – symptoms

Every effort should be made to collect Level 1 evidence of any AE. If an AE has all three levels of evidence, an AE should be reported only once at the highest level of severity, which is the final diagnosis (Level 1). A single AE should not be reported as multiple AEs based on separate symptoms, signs, and diagnosis.

In cases where a diagnosis is not possible, AE determination should be based on the next highest level of evidence (signs, Level 2), followed by symptoms (Level 3), if only symptoms are available.

A corrective action itself is not an AE. The AE should always be determined based on the reason that a corrective action was taken.

Note: there may be multiple symptoms representing or associated with only one AE. In this case only one AE should be reported. The symptoms can be captured within the AE description. If the symptoms are related to LUTS, complete the LUTS form in addition to the AE form. If AE requires catheterization, then complete the catheterization form.

Figure 7-1 is an AE determination and outcome flowchart.

[figure not shown]

Figure 7-1: AE Determination and Outcome Flowchart

Examples

Subject is diagnosed with urinary retention and requires catheterization for more than 3 days. In addition, they have symptoms of irritation, urgency, and hematuria. Only one AE – retention should be reported. The additional symptoms should be noted in the AE description. Catheterization is the treatment.

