14.2 STATISTICAL ANALYSIS

Descriptive statistics will be calculated and reported for study variables, as appropriate. Continuous variables (e.g., symptom score, uroflowmetry, quality of life assessments) will be summarized using statistics such as means, standard deviations and absolute change from baseline. Categorical variables (e.g., adverse events) will be summarized as frequency

distributions. Adverse events and technical observations will be reported by frequency of occurrence, severity and relationship to the vapor treatment device.

All subjects enrolled in this study (including those withdrawn from the study or lost to follow-up) will be accounted for and documented.

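### Section 7.7 gives Definite a weaker test than Probable or Possible and lets Unlikely and Not related overlap, so relationship grades in the 14.2 AE summary are ambiguous unless a precedence rule is documented

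*Combined protocol and SAP*

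**What the plan says.** Section 7.7 sets out five relationship grades and says that the relationship will "be determined by the Principal Investigator using the following definitions".

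- **Definite.** "Definite: The AE follows a reasonable temporal sequence from the time of index procedure". A second sentence brings in events during the procedure and during follow-up. Other causes are not mentioned.
- **Probable.** The same timing, and other factors, "such as underlying disease, concomitant drugs, or concurrent treatment can be excluded".
- **Possible.** The same timing, and a role for the procedure that cannot be ruled out. It continues: "However, other factors such as underlying disease, concomitant medications, or concurrent treatment are presumable".
- **Unlikely.** An improbable sequence, "or it can be reasonably explained by other factors, including underlying disease, concomitant medication, or concurrent treatment". Either condition is enough on its own.
- **Not related.** Again one of two conditions is enough: "The AE has no temporal sequence from the time of the index procedure, or it can be explained by other factors". The same kinds of factor are then listed.

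Section 7.6 requires the relationship to be entered on the AE form for every AE. Section 14.2 then uses it: "Adverse events and technical observations will be reported by frequency of occurrence, severity and relationship to the vapor treatment device".

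Section 7.1 also says: "Figure 7-1 is an AE determination and outcome flowchart". Section 7.7 does not refer to that figure. Neither its content nor the AE form was available to check.

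**The concern.** On a causality scale the conditions should tighten as the claimed certainty rises, and each event should fall in one grade. Here the top grade asks for least among the three upper grades, and the two lowest grades share a criterion.

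The overlaps are not remote in this study. Under 4.1, Phase 1 subjects go on to their planned prostate surgery after vapor treatment. Any AE recorded there has a concurrent treatment as a competing explanation with close timing. In Phase 2, urinary symptoms that last beyond 72 hours count as AEs under 7.1, in men whose underlying disease produces such symptoms.

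Further documenting safety is a Phase 2 objective (5.1). A reader of the relationship summary would need to know what Definite or Not related means in it, and 7.7 does not settle that.

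**Working it through.** The plan gives no figure to reproduce here and no AE counts, so the check is a logical comparison of the five definitions in 7.7.

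| Grade | Timing | Link | Other factors or procedure involvement |
|---|---|---|---|
| Definite | reasonable | – | no condition |
| Probable | reasonable | and | other factors excluded |
| Possible | reasonable | and | involvement not excludable, other factors presumable |
| Unlikely | improbable | or | reasonably explained by other factors |
| Not related | none | or | explained by other factors |

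**Step 1, upper grades.** Write T for reasonable timing. Definite = T. Probable = T and a condition. Possible = T and two conditions. Anything that satisfies T and more also satisfies T. Every Probable AE and every Possible AE therefore meets Definite.

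**Step 2, lower grades.** Both have an *or* limb for other factors. An AE that can be reasonably explained can also be explained, so any AE that meets that limb of Unlikely meets the matching limb of Not related, whatever its timing.

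**Step 3, both ends together.** Take an AE with reasonable timing that underlying disease reasonably explains. Timing alone gives Definite. The explanation gives Unlikely and Not related. If an explained event also counts as having presumable other factors, and procedure involvement cannot be excluded, Possible is met too. The text does not say whether it does.

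**Step 4, what an unwritten rule would do.**

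- Record the highest grade met: Probable and Possible are never used, and the AE in step 3 becomes Definite.
- Record the lowest grade met: the same AE becomes Not related.

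The two rules move the same event in opposite directions, so no net direction follows from the text.

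**Step 5, reach.** The summary covers at most 20 (Phase 1, section 4.3) + 15 (Phase 2, section 5.2) = 35 subjects. The number of AEs, and how many would fall in an overlap, cannot be derived.

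**The case against.** The strongest reply is practical. One Principal Investigator at a single center does the grading, so disagreement between raters is not the issue. The five labels are ordered and have ordinary meanings, and a clinician is unlikely to apply Definite so literally that Probable and Possible become redundant. Section 8 provides training in the protocol and in data collection, and sections 11.10 and 12 provide queries and monitoring. Figure 7-1 or the AE form might carry a rule.

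Much of this stands as mitigation. It makes consistent grading plausible, and it limits what can be said about the final table. It does not supply a written rule. If the investigator grades by ordinary meaning, the grades rest on something other than the definitions that 7.7 says are to be used. Section 8 does not name causality grading among its topics.

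A reader might go further and infer that the safety table is uninterpretable. The documents do not support that: frequency and severity are reported as well and are untouched, and a documented rule would resolve the relationship grades. A reader might also infer that device-related events will be overcounted because Definite is so easy to meet. Step 4 of the working shows that the lower-grade overlap can pull the other way.

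**Conclusion.** The wording defect is established on the face of 7.7. Definite has the weakest test of the three upper grades, Unlikely and Not related overlap, and one AE can qualify at both ends of the scale. The consequence is narrow: relationship grades in the descriptive summary under 14.2 are ambiguous unless a rule is documented. Size and direction cannot be quantified. Severity is minor.

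This rests on two assumptions: that the definitions are read as written, and that neither Figure 7-1 nor the AE form contains a precedence rule. If either does, what remains is to bring 7.7 into line with it.

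Two stronger readings are not supported. The second sentence of Definite might be taken to make every event during follow-up (up to 5 years in Phase 2) Definite. It can also be read as only naming the period covered, with reasonable timing still required; the wording should be made clear. A reader might also infer that safety reporting or the decision on what counts as an AE is distorted. The documents do not say that the 7.7 grades govern those decisions, so no effect there is shown.

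**What to change.** Change 7.7 and the AE form as follows.

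1. **Definite.** Require at least the Probable conditions (reasonable sequence, other causes excluded) plus a stated positive causal criterion, such as direct evidence linking the event to the procedure. Reword the second sentence so that occurrence during follow-up does not qualify an event by itself.
2. **Lowest grades.** Unlikely: the sequence is improbable, or another cause is more likely but does not fully explain the event. Not related: there is no temporal sequence, or another cause fully explains the event.
3. **One grade per AE.** Test Not related, Unlikely, Definite, Probable, Possible in that order and record the first grade met.

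The order matters because the revised wording still leaves overlaps. With reasonable timing and a more likely but incomplete alternative cause, an AE can meet both Unlikely and Possible; the order gives Unlikely. An AE that meets the new Definite also meets Probable; the order gives Definite. To avoid a gap, presumable in Possible should be stated to mean not excluded. The sponsor should also say how to grade an AE with reasonable timing when procedure involvement is excluded but no other cause is more likely or fully explains it. Other schemes would serve if they give one grade per event.

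The cost is protocol and AE form wording, written concurrence between sponsor and Principal Investigator and ethics committee approval under 11.4, and re-review of any relationship grades already recorded. No extra subjects, visits or procedures are needed.

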7.8 DEGREE OF SEVERITY

The degree of severity of the AE to the subject's health will be determined by investigator and documented on an Adverse Event CRF:

Minimal: Awareness of the event but easily tolerated

Moderate: Discomfort enough to cause interference with usual activity

Severe: Inability to carry out usual activity

8 TRAINING

The training of appropriate clinical site personnel will be the responsibility of NxThera, as the study Sponsor. All physicians proctored by NxThera or another trained physician must sign the site Proctoring Form. To ensure proper surgical technique, uniform data collection and protocol compliance, NxThera will present a formal training session to study site personnel. At this training session, the study protocol, techniques for the identification of eligible subjects, instructions on data collection, schedules for follow-up and regulatory requirements will be reviewed.

9 DEVICE MALFUNCTIONS

All failures and malfunctions of the study device must be documented on the Device malfunction/Performance CRF and faxed to the Sponsor, preferably within 24 hours of knowledge of the event. In the event of a device malfunction every effort must be made to return the suspected device to the Sponsor for analysis. All device performance issues and malfunctions will be reported in the clinical results (e.g. final report).

10 STUDY MANAGEMENT

This study is being conducted following "good clinical practices" (GCP). The Sponsor or a Sponsor representative will monitor the progress of the study as required by GCP and as specified by the study monitoring plan. This monitoring will include routine, periodic visits to study sites to compare reported results with source documentation.

10.1 SUBJECT IDENTIFICATION

Subjects participating in the study will be assigned a unique identification code (ID) using the format "XXX-YYY" where:

XXX = Institution Number, assigned by the Sponsor to each study site

YYY = Enrollment Number, assigned by the institution as each subject is enrolled in the study.

CONFIDENTIAL: Contains Proprietary Information

In addition to the ID, each subject's initials will be used as an identifier included on documentation submitted to the Sponsor.

For Phase 1 Acute subjects, an "A" will be added as a Prefix to the subject ID.

For Phase II Optimization subjects, an "O" will be added as a Prefix to the subject ID.

10.2 CENTRAL DATABASE

All study documentation will be collected and compiled in a central database by the Sponsor. Appropriate quality control measures will be established to ensure accurate and complete transfer of information from the study documentation to the central database.

11 REGULATORY RESPONSIBILITIES

11.1 ETHICS COMMITTEE (EC) APPROVAL

The Principal Investigator must submit the study protocol to their EC and obtain the EC's written approval before being allowed to conduct and participate in the study. The Principal Investigator also is responsible for fulfilling any conditions of approval imposed by the EC, such as regular reporting, study timing, etc. The Principal Investigator will provide Sponsor or its designee with copies of such approvals and reports.

11.2 INFORMED CONSENT FORM (ICF)

The Sponsor will provide a template ICF to each site for EC submission. This template may be modified to suit the requirements of the individual study site. The Sponsor must pre-approve all changes to the ICF prior to initial submission to the EC.

The Principal Investigator or assigned designee must administer the EC -approved version of the ICF to each prospective study subject, and obtain the subject's signature or a legally approved designee's signature along with the date of consent prior to enrollment in the study. Subjects must be informed about their right to withdraw from the study at any time and for any reason without sanction, penalty, or loss of benefits to which the subject is otherwise entitled and also informed that withdrawal from the study will not jeopardize their future medical care. A copy of the signed ICF must be given to each subject enrolled in the study.

11.3 CONFIDENTIALITY

All information and data sent to the Sponsor concerning subjects or their participation in this study will be considered confidential. Data used in the analysis and reporting of this evaluation will be used in a manner without identifiable reference to the subject. The Principal Investigator consents to the visits by the staff of the Sponsor and its authorized representatives and the U.S. FDA or any other local governmental body to review the study subjects' medical records, including any test or laboratory data that might have been recorded on diagnostic test media (e.g., cystograms).

11.4 AMENDING THE PROTOCOL

Neither the Principal Investigator nor the Sponsor will modify the Investigational Protocol without first obtaining concurrence of the other in writing. All changes must be submitted to the EC for review and approval. Any change that would require alteration of the ICF must receive approval from the EC prior to implementation. Following approval, the protocol amendment will be distributed to all protocol recipients at the site.

11.5 PROTOCOL DEVIATIONS

A Protocol Deviation CRF must be completed for each study protocol deviation (e.g., failure to obtain informed consent, enrolling a subject who does not meet inclusion / exclusion criteria, not performing required testing, missed follow-up window, etc.). An investigator must notify the Sponsor and the reviewing EC of any deviation from the Study Protocol that was done to protect the life or physical well-being of a subject. Such notice should be given as soon as possible, but no later than five working days after the emergency occurred.

11.6 SITE NONCOMPLIANCE

Repeat serious protocol deviations will be closely monitored. If excessive deviations or a failure to reduce deviations are noted, the Sponsor reserves the right to suspend study enrollment at that site until a sufficient system is in place at the site to reduce further deviations (21 CFR §812.46(a)).

11.7 DEVICE ACCOUNTABILITY

A Device Tracking Log (DTL) will be maintained at each investigational site and will be provided by the Sponsor. The BPH Rezūm Systems and Delivery Devices allocated for investigational site use will be recorded in the log upon delivery to the investigational site and will be stored in a secured area until use. Each site will be responsible for tracking the receipt and disposition of all investigational BPH Rezūm Systems and Delivery Devices. All unused BPH Rezūm Systems and Delivery Devices at the end of the study must be returned to the Sponsor.

The DTL will be updated as each BPH Rezūm System is delivered, used, or returned. The DTL will contain delivery dates, used dates, returned-to-sponsor dates, serial numbers, expiration dates and model and/or unit numbers of the BPH Rezūm Systems and/or Delivery Devices delivered to the site, and the subject IDs associated with all BPH Rezūm Systems and /or Delivery Devices that are used.

11.8 SPONSOR RESPONSIBILITIES

NxThera, Inc. is the Sponsor of this study. NxThera's responsibilities in the study include:

- Provide training to Principal Investigator, other physicians, and the staff of the study site.
- Select the Principal Investigator, all clinical investigators and study sites, and other consultants (e.g., monitors) who participate in the study.
- Provide financial support to each study site.
- Ensure completion of site monitoring of clinical data at clinical study sites.
- Retain ownership of all clinical data generated in this study, and control the use of the data for appropriate purposes only.

11.9 PRINCIPAL INVESTIGATOR RESPONSIBILITIES

The Principal Investigator is responsible for ensuring the investigation is conducted according to all signed agreements, the study protocol and applicable laws and regulations. Also, the Principal Investigator may not begin enrollment until Sponsor or its designee receives and approves (when necessary) the following documents:

- Signed Investigator Agreement

CONFIDENTIAL: Contains Proprietary Information

- **Financial Disclosure Forms for all participating investigators**
- **EC Roster**
- **EC Protocol and ICF Approvals**
- **Investigators' current curricula vitae (CV)**
- **Signed Site Delegation Log**

11.10 CASE REPORT FORMS (CRFS)

CRFs are used to record study data and are an integral part of the study and subsequent reports. Therefore, the data must be legible and complete.

**CRFs will be provided by the sponsor representative via eDC.
All subject questionnaires will be provided by the sponsor representative as paper CRFs.**

MRI Core Lab Forms will be provided by the sponsor representative as paper CRFs. These will then be sent to Libra Medical for data entry into the database.

All paper CRFs must be completed using a pen. Corrections of data on the CRF should be made by crossing out, but not obliterating, the incorrect data with a single line; writing the correct value next to that crossed out; and, at each change, initialing and dating by the person making the change. Correction fluids and covering labels must not be used. If the original CRFs have already been submitted to the data management, the Sponsor will initiate a Data Clarification Form to be completed by study site personnel.

eCRFs must be signed by the study investigator.

Queries will be created in the database if there are missing data or if there is a question about the data submitted following a data review. The site representative will answer the query or correct the data accordingly. The query must be approved by a monitor, data manager or project manager.

12 MONITORING PROCEDURES

The site will be monitored to ensure compliance during the study. Monitoring will consist of review of subject records, source documents, and other required documentation, including EC approvals and correspondence. The site staff must be available to meet with the monitor or other study Sponsor representative during site visits.

The monitoring will be performed in accordance with study Monitoring Plan. The monitoring will be done by the Sponsor representative:

**Libra Medical, Inc.
[name]
[contact]
[contact]
Email: [contact]**

13 REPORTS AND RECORDS

13.1 REPORTS

Table 13-1 displays a list of the reports that are the responsibility of the Principal Investigator to report to the Sponsor. Each study investigator must follow their site’s reviewing EC reporting requirements. If applicable regulations or EC requirements mandate stricter reporting requirements than those listed, the stricter requirements must be followed.

Table 13-1: Reports Required from Investigators to Sponsor

Type of Report	Time Constraints of Notification (from the time study site personnel learned about the event)
Subject death	Written reports (e.g., via e-mail) within 48 hours
SAE or UADE	Within 10 working days
Report of subject enrollment	Daily
Subject withdrawal	Within 5 working days (e.g., by fax, e-mail)
Withdrawal of EC approval	Immediately by telephone/e-mail followed by a copy of the notification within 5 working days
Significant deviations from Study Protocol	Within 5 working days
Informed consent not obtained	Within 5 working days

13.2 RECORDS

The Principal Investigator must maintain the following accurate, complete, and current records relating to the conduct of the investigation. The final responsibility for maintaining such records remains with the Principal Investigator. These include:

- All correspondence with another investigator, an EC, a laboratory, Sponsor or its designee (e.g., monitor);
- Records of each subject’s case history, including study-required CRFs, signed ICF, all relevant observations of AEs, the condition of each subject upon entering and during the course of the investigation, relevant medical history, the results of all diagnostic testing, etc.;
- Study personnel visit log;
- Any other records that applicable regulation requires to be maintained

